10.9. Analysis of Secondary Objectives

For Local Control and Overall Survival, the median and the corresponding two-sided 95% confidence intervals will be calculated using the Kaplan-Meier method. Estimates and 95% confidence intervals will also be provided for 6 and 12 months.

For quality of life measures and neurocognitive assessments, appropriate subscales will be calculated at each time point, along with change from baseline to 3, 6, and 12 months, and summarized descriptively by cohort. Baseline Karnofsky Performance Status and change from baseline to 1, 3, 6, and 12 months will also be summarized and reported by cohort. Summary descriptive statistics only (i.e. no inferential statistics) will be used for all measures except for HVLT-R. An analysis will be done for HVLT-R to use the change from baseline results and compare them to the results generated from the RTOG 0933 study. Wilcoxon Rank Sum Tests will be used for this comparison.

All safety data will be listed. For the treatment-emergent AEs, namely AEs started or worsened during the on-treatment period, the incidence will be summarized by system organ class and/or preferred term, severity based on CTCAE grades, type of adverse event and the relation to the study drug. Deaths reportable as SAEs and non-fatal serious adverse events will be listed by and tabulated by type of adverse event. This will be done with the safety set.

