Several approaches have been explored to decrease the risk of neurocognitive toxicity secondary to WBRT. Presently, many radiation oncologists favor the use of SRS alone followed by close observation and salvage SRS as needed, with WBRT reserved for salvage treatment of diffuse intracranial recurrence. This approach is supported by the previously described studies of SRS +/- WBRT, which did not identify any overall survival advantage to SRS + WBRT despite the presence of a significant local and distant brain control benefit. Furthermore, these trials suggested that SRS alone was associated with improved neurocognitive outcomes. However, the SRS-alone approach has the disadvantage of higher in-brain distant failure rates at 12 months of 55-63.7% with SRS alone vs 27-41.5% when WBRT + SRS is used[5, 6]. A pooled analysis by Tsao et al. again demonstrated a statistically significant local and in-brain distant control benefit favoring WBRT + SRS over SRS alone, with hazard ratios of 2.61 and 2.15, respectively[19].

Another strategy to decrease the risk of neurocognitive toxicity due to whole brain radiation therapy was studied by RTOG 09-33, a phase II trial investigating the role of hippocampal avoidance in WBRT. The hippocampus is crucial for memory formation and hippocampal radiation is thought to contribute significantly to memory impairment in patients undergoing brain radiation. Thus, Gondi et al. demonstrated that in RTOG 09-33 there was a significant improvement in Hopkins Verbal Learning Test-Revised Delayed Recall at 4 months. While these results were significant and encouraging, criticisms of this study include the fact that only 42 of 113 patients were analyzable (likely due to patient dropout from death), the estimated 5% chance of failure at the hippocampal region, the comparison against historical controls, and the use of only one time point for assessment[20].

Brown et al. reported on RTOG 06-14 in which patients were randomized to WBRT with or without the addition of memantine, a drug thought to be protective against neurocognitive decline. Neurocognitive function was measured by multiple subtests of the Hopkins Verbal Learning Test – Revised (HVLT-R). The trial demonstrated a trend toward improved cognitive function with the addition of memantine that was not statistically significant, possibly due to the fact that only 149 of 508 patients were analyzable at the prespecified analysis point of 24 weeks[21].

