10. STATISTICAL METHODS

10.1. General Considerations

Statistical analysis of this study will be the responsibility of the Department of Biostatistics at Indiana University School of Medicine. Parameter estimates and relevant summary statistics will be reported for both efficacy and safety outcomes. Continuous variables will be summarized by means, medians, minima, maxima and standard deviations. Categorical variables will be summarized by frequencies and percentages. Missing data will not be imputed. Additional exploratory analysis will be conducted when appropriate. Changes from the analysis plan will not require an amendment to the protocol unless it changes a significant feature in the protocol. The statistical analysis methods are outline below.

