10.4.3. Efficacy Population

The efficacy population comprises all subjects who have received at least one dose of radiation, and have been evaluated for the primary endpoint (the 6 month scan). This population will be used for efficacy analysis.

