10.5. Sample Size

A total sample size of 20 evaluable subjects per cohort was determined to balance the competing goals of assessing the primary objective while not exposing more subjects to an investigational decreased radiation procedure than is required. Historical data has shown that approximately 20% of subjects with standard radiation treatment show in-brain distant failure at 6 months. This trial is looking to see if decreased radiation will provide similar efficacy to the standard of care. There will be an interim analysis after the first cohort completes their 6 month scans. If less than 20% of the subjects have in-brain distant failure, then the second cohort will start.

With 20 evaluable subjects in a cohort, the 90% confidence interval around the proportion of subjects who are expected to have in-brain distant failure at 6 months would extend at most +/- 14.7%. Up to 25 subjects may be enrolled in each cohort. Although subjects who die before 6 months without confirmed in-brain distant failure would be replaced if possible, the following table will show the estimated confidence interval widths assuming the 20% proportion of subjects who may have in-brain distant failure at 6 months:

Number of Patients:	15	20	25
90% Confidence interval width:	17.0%	14.7%	13.2%

As stated in section 7.1.9, patients will not be considered evaluable if the sum total of radiotherapy interruptions exceeds 3 normally scheduled treatment days.

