TENT			mountain			cat*			HOTEL			COW			diamond*		

4. Discontinued: Testing discontinued? Yes (Complete the Neurocognitive Tests Discontinued/Not Done CRF)

No

RETAIN DATA SHEETS IN PATIENT STUDY FILE

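### HVLT-R and FACT-Br change is summarised only in patients with an observed score, so cognition and quality of life are liable to look better preserved than they are

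*Combined protocol and SAP*

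**What the plan says.** Section 3.2 defines the neurocognitive, quality-of-life and performance-status outcomes as change from baseline at 6 months. It does not say how death or inability to be tested is handled.

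Section 10.9 gives the analysis. HVLT-R and FACT-Br scores are calculated at each time point, "along with change from baseline to 3, 6, and 12 months, and summarized descriptively by cohort". For performance status, "Baseline Karnofsky Performance Status and change from baseline to 1, 3, 6, and 12 months will also be summarized and reported by cohort". One inferential use is planned: "An analysis will be done for HVLT-R to use the change from baseline results and compare them to the results generated from the RTOG 0933", by Wilcoxon rank sum test. Section 10.1 sets the missing-data rule: "Missing data will not be imputed".

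Two other provisions affect who contributes. The efficacy population (10.4.3) is limited to treated patients who "have been evaluated for the primary endpoint (the 6 month scan"). Section 10.5 adds: "Although subjects who die before 6 months without confirmed in-brain distant failure would be replaced if possible".

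Section 1.2 lists among the criticisms of RTOG 09-33 that "only 42 of 113 patients were analyzable (likely due to patient dropout from death"). Section 1.4 says that a battery which impaired patients can complete reduces selection in favour of those who will do well. The sample HVLT-R sheet in Appendix 4 carries a prompt for when testing is discontinued: "Complete the Neurocognitive Tests Discontinued/Not Done CRF". No analysis section refers to that form.

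**The concern.** A change score exists only for a patient who is alive and was tested. With no imputation and no other summary, the 6-month HVLT-R and FACT-Br results describe that subset alone. A patient who can no longer do the word-list test or fill in the questionnaire because of neurological decline has the very outcome that secondary objectives 3 and 4 ask about, yet does not appear in the result.

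Section 1.6 presents the trial as a search for a balance between cognitive deficit from whole-brain dose and cognitive deficit from new or progressing lesions. Patients with uncontrolled lesions are plausibly among those who become untestable, so the planned summary could miss part of the harm side of that balance. Section 5 says neurocognitive outcomes would be included in the next trial, so a flattering pilot result could carry forward.

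If HVLT-R and FACT-Br are treated as efficacy analyses, the 6-month-scan requirement would narrow the denominator further. It would also remove the 3-month scores of patients who never reach that scan.

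**Working it through.** **The plan's own figures.** The only sizing calculation is for in-brain distant failure. It reproduces: 1.645 × √(0.2 × 0.8 / n) gives 17.0%, 14.7% and 13.2% for n = 15, 20 and 25, as section 10.5 states. Nothing is sized for HVLT-R, FACT-Br or KPS, so there is no planned number of scored patients to check against.

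**Inputs for an illustration.**
- Enrolment cap per cohort: 25 (section 10.5).
- Testing compliance at 6 months in a cited trial: 77-87% (section 1.4). I assume this is a share of patients alive.
- Median survival: 6.9, 9.2, 15.2 and 25.3 months, taken from Table 16-2. The first is the lowest score-band median in that table that is not below the 6-month life-expectancy limit in section 4.2. Applying these values to this trial is an assumption.
- Exponential survival (assumption): S(6) = 0.5^(6/median).

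**Expected split of 25 patients at 6 months.** Dead = 25 × (1 − S). Tested = 25 × S × compliance. Alive but untested = 25 × S × (1 − compliance).

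| Median (months) | S(6) | Tested | Alive, untested | Dead |
|---|---|---|---|---|
| 6.9 | 0.547 | 10.5-11.9 | 1.8-3.1 | 11.3 |
| 9.2 | 0.636 | 12.2-13.8 | 2.1-3.7 | 9.1 |
| 15.2 | 0.761 | 14.6-16.5 | 2.5-4.4 | 6.0 |
| 25.3 | 0.848 | 16.3-18.5 | 2.8-4.9 | 3.8 |

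So about 10 to 19 of 25 patients would have a 6-month score.

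**Bias among patients alive at the visit.** Let u be the untested share of the living (13-23%), and delta the amount by which untested patients would have scored worse than tested ones. The tested-only mean is too favourable by u × delta.
- delta = 0: no bias.
- delta = 0.5 SD: 0.13 × 0.5 to 0.23 × 0.5, about 0.07 to 0.12 SD.
- delta = 1 SD: 0.13 to 0.23 SD.

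The documents give no value for delta. I leave the dead out of this formula, because they have no 6-month cognition to be biased about; they belong in a separate count.

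**What lowest-ranking would do.** If every untested living patient were untestable because of decline (the extreme case), the median over the living would fall at the (0.5 − u)/(1 − u) quantile of the observed scores: 0.37/0.87 = 0.43 at u = 0.13, and 0.27/0.77 = 0.35 at u = 0.23. The median would still be an observed score.

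**KPS.** Section 3.2 treats KPS as a clinical assessment, and the scale in Appendix 2 runs down to 10 (moribund). An impaired patient can still be scored, so only death and missed visits leave a gap.

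**The case against.** The best case for the plan is that this is a non-randomised pilot. FACT-Br and KPS are purely descriptive, and no cognitive result decides whether Cohort B opens or the study stops. Patients with short life expectancy or unable to complete the assessments are excluded (4.2), HVLT-R may be given remotely, and FACT-Br may be completed at home. All of that stands and limits the consequence. It does not supply a denominator for the summaries.

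Several stronger readings are tempting, and the documents do not support them.
- A reader might infer that cognition is bound to look preserved. That needs missingness to track cognition. Section 1.1 says adequately treated patients usually die of non-neurologic causes (34.4% against 20.6% at 6 months in its cited series), and section 1.2 attributes the RTOG 09-33 losses to probable death.
- A reader might carry over the analysable shares in section 1.2, 42/113 = 37% and 149/508 = 29%, and expect 0.29 × 20 to 0.37 × 25, or roughly 6 to 9 scored patients. That ignores the eligibility limits here and the 77-87% compliance figure.
- A reader might say that deaths and dropouts are not reported at all. They are: 10.7 summarises discontinuation reasons by cohort, and 10.9 gives Kaplan-Meier survival at 6 and 12 months. Neither is linked to test status at a visit.
- A reader might infer that the RTOG 0933 comparison favours this trial. That study was also limited to analysable patients, so the net bias could go either way.

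**Conclusion.** The concern holds for HVLT-R and FACT-Br. Sections 3.2, 10.1 and 10.9 together produce a summary of observed scores only, and no section keeps patients untestable because of decline in view. The within-cohort results are therefore liable to look better than the truth, by the reasoning the protocol itself gives in sections 1.2 and 1.4. For KPS the point reduces to death and missed visits.

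The size is not derivable from the documents. Under the stated survival and compliance assumptions, about 10 to 19 of 25 patients would have a 6-month score. Among the living, the tested-only mean would be too favourable by 0 to about 0.23 SD as delta runs from 0 to 1 SD. The change is worth making, but it does not affect the primary endpoint or the decision to open Cohort B.

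**What to change.** In section 10.9, keep the planned summary of observed scores and add, for all treated patients by cohort:

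1. At each visit, counts of tested; alive but untested because of neurological or physical decline; alive but untested for other reasons; and dead. For KPS, scored, missed and dead are enough. The reason for a missing test must be recorded prospectively. Confirm that the discontinued/not-done form named in Appendix 4 is in use and captures it: section 7.2.1 describes that appendix as a sample, and the form itself is not in the documents.
2. A within-cohort descriptive sensitivity summary of HVLT-R change (for example the median) among patients alive at the visit, ranking those untestable because of decline below every observed score. Do not use it in the Wilcoxon comparison, because re-ranking only this trial's patients would make the two sides unlike.
3. Baseline scores of patients with and without the 6-month test.

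Also state that the RTOG 0933 comparison is between analysable patients only and could be biased in either direction.

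The cost is SAP wording, a small table, and possibly one added field for the reason a test was not done. It needs no extra patients or visits. The downside is that the reported cognitive result may be less favourable.

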10.10. Analysis of Exploratory Objective

The biomarkers of circulating tumor DNA and microRNA in blood and urine, both pre-treatment and changes over time, will be correlated with treated lesion control, in-brain distant control, and overall survival using Cox proportional hazards regression. Time dependent ROC curves will be generated to assess predictive ability.

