3.3. Exploratory Outcome Measure

Generate data for sample size estimates for a future prospective study.

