10.8. Analysis of Primary Objectives

All analyses will be done by cohort. For the primary objective, the number of patients who have in-brain distant failure in the evaluable patients will be summarized and exact binomial 95% confidence intervals will be determined.

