10.11. Interim Analysis

After the first cohort completes the 6 month scans, an interim analysis will be conducted. If less than 20% of the patients have in-brain distant failure, then the next cohort will begin enrollment. If 20% or more of the patients have in-brain distant failure, then the study will stop.

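### Section 10.10 judges biomarker prediction in-sample, with no marker list, pooling rule or optimism correction stated; at most 3 distant failures in a passing cohort of 20 make the best apparent AUC unreliable for planning

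*Combined protocol and SAP*

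**What the plan says.** Section 10.10 is the whole biomarker analysis. Circulating tumor DNA and microRNA in blood and urine, as pre-treatment values and as changes over time, are related by Cox regression to treated lesion control, in-brain distant control and overall survival. Then "Time dependent ROC curves will be generated to assess predictive ability". No number of markers, limit on covariates, multiplicity rule, validation, optimism correction or interval for the AUC is given, and the general methods in 10.1 supply none.

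On the unit of analysis, section 10.8 says "All analyses will be done by cohort". Section 10.10 is silent on pooling.

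On size, section 10.5 says "A total sample size of 20 evaluable subjects per cohort was determined" and "Up to 25 subjects may be enrolled in each cohort". Section 10.11 says "If less than 20% of the patients have in-brain distant failure, then the next cohort will begin enrollment".

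On purpose, section 2.3 sets out to identify markers that could become a predictive blood or urine test, and section 3.3 gives the exploratory outcome measure as "Generate data for sample size estimates for a future prospective study". Under section 7.5 the sampling is optional.

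**The concern.** An AUC computed on the patients in whom the marker was identified is biased upward. The bias grows with the number of markers examined and shrinks with the number of events. Here the events for distant control are very few by construction, because the study moves to Cohort B only when distant failure in Cohort A is under 20%. The number of markers is left open.

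What is at stake is the one use that section 3.3 names. If the best apparent AUC or hazard ratio were taken as a planning value, the later study could be too small or built around a marker with no real signal. The primary result of this trial is not affected.

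**Working it through.** **The plan's own figure.** The only sizing in 10.5 is for the primary proportion, with a 90% interval that "would extend at most +/- 14.7" percentage points. The Wald half-width 1.645 × √(0.2 × 0.8 / n) gives 17.0, 14.7 and 13.2 points for n = 15, 20 and 25, matching the table in 10.5. No such figure is given for the biomarker aim.

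**Events available.** The largest x with x/n below 0.20 is 2 of 15, 3 of 20 or 4 of 25. Two just-passing cohorts of 20 give 6 of 40. Optional sampling can lower these counts.

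**Number of predictors (assumption).** The documents give no count. Section 7.5 lists six sampling points: baseline, day 1 before and after treatment, day 5, last day, and 1 month. Two analytes × two fluids × (1 baseline + 5 changes) = 24 per endpoint if all microRNA counts as one marker. I show 4, 12 and 24.

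**One noise marker.** With e events among n patients, the null SD of the AUC is √[(n + 1) / (12 e (n − e))]:
- 3 of 20: √(21/612) = 0.185
- 4 of 25: √(26/1008) = 0.161
- 6 of 40: √(41/2448) = 0.129

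The exact rank-sum distribution, counting either direction, gives the chance q that one noise marker reaches 0.80: 11.8%, 5.7% and 1.7% respectively.

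**Best of m independent noise markers.** The chance that at least one reaches 0.80 is 1 − (1 − q)^m:

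| Events | m = 4 | m = 12 | m = 24 |
|---|---|---|---|
| 3 of 20 | 39% | 78% | 95% |
| 4 of 25 | 21% | 50% | about 75% |
| 6 of 40 | 7% | 19% | about 34% |

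**Mean best AUC, 24 noise markers.** These come from simulation with 6,000 runs, taking the larger of AUC and 1 − AUC for each marker and then the maximum over markers. At 3 of 20 the mean is 0.89 if the markers are independent and 0.86 if every pair is correlated at 0.5. At 6 of 40 it is 0.78 and 0.75. With correlation 0.5 and 3 of 20, just under 80% of runs still contain a marker at or above 0.80.

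**Cox models.** A null hazard ratio per SD has a 95% range of exp(±1.96/√3) = 0.32 to 3.10 with 3 events and exp(±1.96/√6) = 0.45 to 2.23 with 6. For 80% power, the hazard ratio per SD must be about exp((1.96 + 0.84)/√3) = 5.0 with 3 events. In simulation with 3 of 20, a noise marker gives a hazard ratio of at least 2, or at most 0.5, in 27% of runs. The single likelihood-ratio test stays near its level (about 6% at a nominal 5%). Over 24 independent tests, however, the chance of at least one false positive is 1 − 0.95^24 = 71%.

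**Effect of correction.** Resampling that repeats the marker selection brought the mean null AUC to about 0.46 to 0.48, with an SD of about 0.2. The optimism goes; the imprecision stays.

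**The case against.** A reader might infer that noise markers will look strongly predictive and will misdirect the next study. The documents do not support that certainty. One noise marker reaches 0.80 in only 11.8% of cases at 3 of 20, and the best of four does so in 39%. The high figures need about a dozen markers or more, a count found nowhere in the plan, and repeated samples of the same analyte are probably correlated. Section 10.10 describes no explicit selection step, and the lack of correction is read from silence in a short exploratory section. Section 3.3 does not say that the best AUC becomes the planning value, and section 1.6 already looks to later prospective evaluation.

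The by-cohort premise is also limited. The sentence stands under the primary objective. Section 10.9 repeats the by-cohort wording for its own descriptive measures, whereas 10.10 does not. Section 2.3 contrasts patients with and without recurrence or side effects without a cohort split. Pooling is therefore not excluded.

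The limit of 3 events covers only distant failure by 6 months in a passing cohort of 20. Scans run to 12 months (7.4), a failing Cohort A of 20 has 4 or more events, no continuation rule caps Cohort B, and treated lesion control and overall survival are not bound by the rule.

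All of this stands and narrows the point. It does not remove it. Section 2.3 makes identifying markers the aim, nothing commits the analysis to a correction, correlation of 0.5 lowers the mean best AUC only from 0.89 to 0.86, and pooling reduces the optimism without ending it.

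**Conclusion.** The point holds in a limited form and is an improvement worth making. For 6-month distant control, with 3 events in 20 and about a dozen or more markers examined, the best apparent AUC from pure noise can easily reach 0.80. With 24 predictors its mean is about 0.86 to 0.89, or about 0.75 to 0.78 when pooled at 6 of 40. Such values are unreliable for sample-size planning.

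This rests on three assumptions: the marker count, a pairwise correlation between 0 and 0.5, and every enrolled evaluable patient giving samples. Fewer samples would make it worse; later or other events would make it better. For the Cox models the problem is unstable effect sizes and multiplicity, since each single test is close to its nominal level. Harm to the next study is a risk, not a certainty.

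**What to change.** In section 10.10:
- State that the cohorts are pooled, with the Cox baseline hazard stratified by cohort.
- Pre-specify a short primary marker list, and treat every other marker as screening with false-discovery-rate adjustment.
- Report AUCs and hazard ratios with confidence intervals, and with an optimism correction (bootstrap or cross-validation) that repeats any marker selection inside each resample.
- State that uncorrected best-marker values will not be used for the sample-size estimates named in 3.3.

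The cost is a little more programming and an early decision on which markers come first. Reported AUCs will be lower. With so few events the corrected estimates will still be imprecise, and the report should say so. No extra patients or samples are needed.
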